8.3 Ethics and regulatory review

An Ethics Committee should approve the final study protocol, including the final version of the Informed Consent Form and any other written information and/or materials to be provided to the patients. The investigator will ensure the distribution of these documents to the applicable Ethics Committee, and to the study site staff.

The opinion of the Ethics Committee should be given in writing. The investigator should submit the written approval to AstraZeneca before enrolment of any patient into the study.

The Ethics Committee should approve all advertising used to recruit patients for the study.

AstraZeneca should approve any modifications to the Informed Consent Form that are needed to meet local requirements.

If required by local regulations, the protocol should be re-approved by the Ethics Committee annually.

Before enrolment of any patient into the study, the final study protocol, including the final version of the Informed Consent Form, will be approved by the national regulatory authority or a notification to the national regulatory authority is done, according to local regulations.

AstraZeneca together with ICON will handle the distribution of any of these documents to the national regulatory authorities.

AstraZeneca will provide Regulatory Authorities, Ethics Committees and Principal Investigators with safety updates/reports according to local requirements. For studies in countries implementing the EU Clinical Trials Directive, informing Ethics Committees and Regulatory Authorities will be performed by AstraZeneca together with ICON.

Each Principal Investigator is responsible for providing the Ethics Committees/IRB with reports of any serious and unexpected adverse drug reactions from any other study conducted with the IP. AstraZeneca will provide this information to the Principal Investigator so that he/she can meet these reporting requirements.

8.4 Informed consent

The Principal Investigator(s) at each centre will:

- Ensure each patient is given full and adequate oral and written information about the nature, purpose, possible risk and benefit of the study.
- Ensure each patient is notified that they are free to discontinue from the study at any time.
- Ensure that each patient is given the opportunity to ask questions and allowed time to consider the information provided.
- Ensure each patient provides signed and dated informed consent before conducting any procedure specifically for the study.
- Ensure the original, signed Informed Consent Form(s) is/are stored in the Investigator's Study File.
- Ensure a copy of the signed Informed Consent Form is given to the patient.
- Ensure that any incentives for patients who participate in the study as well as any provisions for patients harmed as a consequence of study participation are described in the informed consent form that is approved by an Ethics Committee.

8.5 Changes to the protocol and informed consent form

Study procedures will not be changed without the mutual agreement of the International co-ordinating Investigator, National Co-ordinating Investigator, and the Principal Investigator and AstraZeneca.

If there are any substantial changes to the study protocol, these changes will be documented in a study protocol amendment and where required in a new version of the study protocol (Revised Clinical Study Protocol).

The amendment should be approved by each Ethics Committee and if applicable, also the national regulatory authority, before implementation. Local requirements should be followed for revised protocols.

AstraZeneca will distribute any subsequent amendments and new versions of the protocol to each Principal Investigator(s). For distribution to Ethics Committee see Section 8.3.

If a protocol amendment requires a change to a centre's Informed Consent Form, AstraZeneca and the centre's Ethics Committee should approve the revised Informed Consent Form before the revised form is used.

If local regulations require, any administrative change will be communicated to or approved by each Ethics Committee.

8.6 Audits and inspections

Authorised representatives of AstraZeneca, a regulatory authority, or an Ethics Committee may perform audits or inspections at the centre, including source data verification. The purpose of an audit or inspection is to systematically and independently examine all study-related activities and documents, to determine whether these activities were conducted, and data were recorded, analysed, and accurately reported according to the protocol, Good Clinical Practice (GCP), guidelines of the International Conference on Harmonisation (ICH), and any applicable regulatory requirements. The investigator will contact AstraZeneca immediately if contacted by a regulatory agency about an inspection at the centre.

9. STUDY MANAGEMENT BY ICON CLINICAL RESEARCH

9.1 Pre-study activities

Before the first patient is entered into the study, it is necessary for a representative of ICON Clinical Research to visit the investigational study site to:

- Determine the adequacy of the facilities.
- Determine availability of appropriate patients for the study.
- Discuss with the investigator(s) (and other personnel involved with the study) their responsibilities with regard to protocol adherence, and the responsibilities of AstraZeneca or its representatives. This will be documented in a Clinical Study Agreement between ICON Clinical Research and the investigator.

9.2 Training of study site personnel

Before the first patient is entered into the study, an ICON Clinical Research representative will review and discuss the requirements of the Clinical Study Protocol and related documents with the investigational staff and also train them in any study specific procedures and the WBDC system(s) utilised.

The Principal Investigator will ensure that appropriate training relevant to the study is given to all of these staff, and that any new information relevant to the performance of this study is forwarded to the staff involved.

The Principal Investigator will maintain a record of all individuals involved in the study (medical, nursing and other staff).

9.3 Monitoring of the study

During the study, an ICON Clinical Research representative will have regular contacts with the study site, including visits to:

- Provide information and support to the investigator(s).
- Confirm that facilities remain acceptable.
- Confirm that the investigational team is adhering to the protocol, that data are being accurately and timely recorded in the eCRFs, that genetic samples are handled in accordance with the Laboratory Manual and that IP accountability checks are being performed.
- Perform source data verification (a comparison of the data in the eCRFs with the patient's medical records at the hospital or practice, and other records relevant to the study) including verification of informed consent of participating patients. This will require direct access to all original records for each patient (eg, clinic charts).
- Ensure withdrawal of informed consent to the use of the patient's biological samples is reported and genetic samples are identified and disposed of/destroyed accordingly, and the action is documented, and reported to the patient.

The ICON Clinical Research representative will be available between visits if the investigator(s) or other staff at the centre needs information and advice about the study conduct.

9.3.1 Source data

For the purpose of this study eCRF and medical journals will act as the source data for all information collected in the study.

9.4 Study agreements

The Principal Investigator at each/the centre should comply with all the terms, conditions, and obligations of the Clinical Study Agreement for this study. In the event of any inconsistency between this Clinical Study Protocol and the Clinical Study Agreement, the terms of Clinical Study Protocol shall prevail with respect to the conduct of the study and the treatment of patients and in all other respects, not relating to study conduct or treatment of patients, the terms of the Clinical Study Agreement shall prevail.

Agreements between ICON Clinical Research and the Principal Investigator should be in place before any study-related procedures can take place, or patients are enrolled.

9.4.1 Archiving of study documents

The Investigator will follow the principles outlined in the Clinical Study Agreement (CSA).

9.5 Study timetable and end of study

The end of the study is defined as “the last visit of the last patient undergoing the study”.

The study is expected to start in Q4 2009 and to end by Q1 2011.

The study may be terminated at individual centres if the study procedures are not being performed according to GCP, or if recruitment is slow. AstraZeneca may also terminate the entire study prematurely if concerns for safety arise within this study or in any other study with AZD1656.

10. DATA MANAGEMENT

Data management will be performed by ICON Clinical Research. Data collected through third party sources (eg, laboratory assessments, ECGs) will be obtained and reconciled against study data.

Adverse events and medical/surgical history will be classified according to the terminology of the latest version the Medical Dictionary for Regulatory Activities (MedDRA). Medications will be classified according to the AstraZeneca Drug Dictionary. All coding will be performed by ICON Data Management.

Data queries will be raised for inconsistent, impossible or missing data. All entries to the study database will be available in an audit trail.

The data will be validated as defined in the Data Management Plan. Quality control procedures will be applied to each stage of data handling to ensure that all data are reliable and have been processed correctly.

When all data have been coded, validated, signed and locked, clean file will be declared. Any treatment revealing data may thereafter be added and the final database will be locked.

Data associated with biological samples will be transferred to laboratories internal or external to AstraZeneca.

Any genotype data generated in this study will be stored in the AstraZeneca genotyping LIMS database, or other appropriate secure system within AstraZeneca and/or ICON Clinical Research to analyse the samples.

The results from this genetic research may be reported in the CSR for the main study, or in a separate report as appropriate.

11. EVALUATION AND CALCULATION OF VARIABLES

11.1 Calculation or derivation of efficacy variable(s)

All data derivations will be performed by ICON Biostatistics.

The mean of SMPG for each day will be computed only if more than half the data collected that day are available (ie, if 4 or more collection point are missing on the 7-point scale the daily mean will be set to missing).

If the assessment (CRF or lab data) is collected more than once for the same visit/time-point, the first assessment will be used in the analysis. If the assessment is outside the visit window then it will still be considered of interest and won't be excluded from the analysis.

For the lab parameters (C-peptide, LDL, HDL, trygliceride, etc.), value reported as <LLOQ will be analysed as LLOQ/2, value reported as > upper limit of quantification (ULOQ) will be analysed as ULOQ.

Change from baseline will be computed as the value at each visit post-baseline – baseline result. Baseline value will be defined as the last non-missing value on or before first dose of treatment. If the value is missing at the randomization visit, the enrolment (screening) result will be used.

Percentage will be based on the number of patient in the respective analysis set.

11.2 Calculation or derivation of safety variable(s)

Events of hypoglycaemia will be categorised into 1 of the following main categories, based on the investigator reported data:

- Major hypoglycaemia: Hypoglycaemic episode where the patient absolutely needed help from another person to recover, due to impaired consciousness or altered behaviour. There should also be documented prompt recovery after treatment with glucose or glucagon, and pre-treatment plasma glucose should be below 3.0 mmol/L or missing.

- Minor hypoglycaemia: Hypoglycaemic episode that the patient was able to manage by self-administration. There should also be a documented plasma glucose below 3.0 mmol/L before treatment.
- Episode suggestive of hypoglycaemia: Any hypoglycaemic episode that the patient was able to manage by self-administration but where pre-treatment plasma glucose is either missing or greater than 3.0 mmol/L.

ECG (12-lead and telemetry): QTc will be derived as:

Bazett:

$$QTc = \frac{QT}{\sqrt{RR}}$$

Frederica QTc

$$QTc = \frac{QT}{(RR)^{1/3}}$$

Where RR (interval from the onset of 1 QRS complex to the onset of the next QRS complex) will be derived as 60/HR with HR been the heart rate.

The GFR will be calculated as:

GFR (mL/min per 1.73m²) = 186 x (SCr)^{-1.154} x (Age)^{-0.203} x (0.742 if female) x (1.210 if African-American) where SCr = serum creatinine concentration inmg/dL, age is in years, and weight is in kg.

11.2.1 Other significant adverse events (OAE)

During the evaluation of the AE data, an AstraZeneca medically qualified expert will review the list of AEs that were not reported as SAEs and discontinuations due to AE (DAEs). Based on the expert's judgement, significant adverse events of particular clinical importance may, after consultation with the Global Patient Safety Physician, be considered OAEs and reported as such in the Clinical Study Report. A similar review of laboratory/vital signs/ECG data will be performed for identification of OAEs.

Examples of these are marked haematological and other laboratory abnormalities, and certain events that lead to intervention (other than those already classified as serious), dose reduction or significant additional treatment.

11.3 Calculation or derivation of patient reported outcome variables

Not applicable.

11.4 Calculation or derivation of pharmacokinetic variables

Not applicable, see Section 11.5.2.

11.5 Calculation or derivation of pharmacodynamic variable(s)

Not applicable, see Section 11.5.2.

11.5.1 Calculation or derivation of the relationship between pharmacokinetic and pharmacodynamic variables

Not applicable, see Section 11.5.2.

11.5.2 Population analysis of pharmacokinetic/pharmacodynamic variables

Population PK/PD modelling of the data will be performed at AstraZeneca R&D, using non-linear mixed effects regression in NONMEM. A semi-mechanistic drug-disease model, describing the interplay between drug concentrations, glucose, HbA1c and insulin levels as well as their time-course, will be applied and fit to data to estimate mean population PK/PD parameters with associated between- and within-patient variability. Also, the influence of patient-specific covariates such as gender, age, body weight, creatinine clearance and disease status on the PK and PD parameters may be investigated. A population PK/PD analysis plan will be written prior to clean file. The modelling results will be provided in a separate population PK/PD report.

11.6 Calculation or derivation of pharmacogenetic variables

Provision of a blood sample for genetic research is optional to study participants. For all obtained samples, the DNA will be extracted from the blood sample. DNA samples will be handled in the coded format and stored for a maximum of 25 years.

The decision to perform a genetic analysis of archived DNA will be based on potential scientific and clinical indication. The potential exploratory genetic analysis will be performed by AstraZeneca R&D, Alderly Park, United Kingdom or at the designated contract laboratory. The genotypic data generated from the study will be stored in the AstraZeneca LIMS database, clinical database or other appropriate system. Accordingly, patients placed into genotype groups will be compared for their respective phenotype (such as response to AZD1656, metformin and glipizide distribution, safety, tolerability and efficacy or susceptibility for T2DM). The results from this genetic research will be reported in a separate report. Some or all of the clinical datasets from the main study may be merged with the genetic data in a suitable secure environment separate from the clinical database.

11.7 Calculation or derivation of health economic variables (Not applicable)

12. STATISTICAL METHODS AND SAMPLE SIZE DETERMINATION

12.1 Description of analysis sets

The following study analysis sets will be defined.

12.1.1 Full analysis set

All randomized patients with at least 1 dose administered, and with at least 1 post-baseline efficacy data, will be included in the Full Analysis Set (FAS).

Patients will be analysed according to the randomized treatment, irrespective of the treatment received.

This will be the primary analysis set used for all efficacy analysis variables.

The Per-Protocol (PP) analysis set will consist of the patients in the FAS who do not violate any major entry condition and do not violate the protocol between randomization and study completion. Major deviations from the protocol procedures include:

- Violation of inclusion/exclusion criteria.
- Disallowed concomitant medication.
- Missing key efficacy data. (ie, Hb1Ac at 4 months or last visit).
- Patient is not compliant

This will be the secondary efficacy analysis set and will be applied to all key efficacy analysis variables.

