Glipizide will be encapsulated into orange hard gelatine capsules and contain glipizide tablets corresponding to a dose of 5mg glipizide or no glipizide tablets if a placebo capsule. The total daily dose of glipizide/ placebo will be composed of 4 capsules, of which up to 4 capsules will contain active compound and rest placebo, depending on the daily dose.

Two tablets AZD1656 and two capsules glipizide will be administered orally in the morning with breakfast and 2 tablets AZD1656 and 2 capsules glipizide will be administered orally in the evening with dinner. Patients randomized to the blinded treatment will take both AZD1656/placebo and glipizide/placebo. Patients assigned to the open dose of AZD1656 will only take 2 tablets of AZD1656 at each dosing event.

Two strengths of metformin tablets, 500mg and 850mg respectively, will be provided by the sponsor. The metformin will be packed in to blister cards, open-label, 100 tablets per package for the 500mg metformin and 56 tablets per package for the 850mg metformin. The dose will be individual but will stay between 1.5 and 3 g per day, administered orally as tablets once, twice or three times daily together with meal.

Duration of study and randomized treatment period

An enrolment visit (screening) will take place approximately 4 weeks before the start of randomized study treatment. Eligible patients will receive randomized treatment for 4 month and those patients consenting also to the 2-month extension will receive randomized treatment for 6 months in total. During the randomized treatment period, visits to the clinic are scheduled on a weekly basis during the initial titration period, followed by visits each month during the maintenance phase up to 4 months, with an optional 2 months extension. A follow-up visit will be scheduled 2 weeks \pm 5 days after the end of treatment visit (or last visit if premature discontinuation).

Outcome variable(s):

Primary outcome variable

- The primary efficacy variable is defined as the change in HbA1c from baseline to the final visit at 4 months. Baseline will be defined as the last non-missing value on or before the first treatment dose received (the HbA1c sample at Visit 3 will be collected prior to the first dose intake). If the value is missing at the randomization visit, the enrolment (screening) result will be used.

Secondary outcome variables

- The time-course of drug concentrations for AZD1656 and its active metabolite AZD12555623 in plasma.

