Patients will have to provide a new informed consent for the extension of the study. Patients will come for monthly visits, Visit 12 at 5 months and visit 13 at 6 months.

Visit 11 (Follow-up visit) and Visit 14 (Follow-up visit -Extension)

Two weeks (± 5 days) after the last visit, the patient will be scheduled in the morning to a final visit. Any ongoing AEs will be followed up as long as medically indicated. Patients will come in fasting and undergo a physical examination, a laboratory screen, ECG, vital signs (BP and pulse) and weight measurement, advice for diet and life style will be given.

Genetic informed consent and blood samples

Patients who take part in the genetic component of the study will be required to give written informed consent prior to blood being drawn. The blood sample for genetic research will be obtained from the patients at Week 0 (Visit 3) after randomization. If for any reason the sample is not drawn at Visit 3, it may be taken at any visit until the last study visit. Only

1 sample should be collected per patient for genetics during the study. The blood draw should not take place prior to randomization.

Unscheduled visit

Extra visits may be necessary for safety reasons. These visits will be recorded in the eCRF as unscheduled visits, necessary safety samples sent to the central lab and AE/SAE section completed as deemed appropriate by the Investigator.

The study assessments are described in the Study plan, [Table 1](#)

Extension of the 4-month study:

At the 4 months visit, the following two options will be offered to study participants:

- Continue as per the original study protocol, with the scheduled follow-up visit 2 weeks after the last dose at 4 months
- Patients can provide informed consent for optional treatment for 2 additional months, ie up to 6 months randomized treatment. Patients consenting to the extension will have their follow-up visit 2 weeks after having taken the last IP at the 6-month visit (or earlier if pre-matured stopped IP) .

All patients consenting to the extended study will continue on the same blinded (or open in cohort 2) treatment as during the 4-month study. Patients, investigators and site monitors will be kept blinded during the whole study. After finalising and cleaning the data in the 4-month study, the sponsor and CRO will be unblinded.

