5.4.2 Methods for unblinding the study

Individual treatment information, indicating the treatment randomization for each randomized patient, will be available to the investigator(s) at the study centre and the personnel who are independent to the study evaluation at the Patient Safety Department from the IVRS/IWRS, in case of a need for emergency unblinding. IVRS/IWRS will provide 24 hours/day 7 days a week unblinding service. Routines for this will be described in the IVRS/IWRS user manual that will be provided to each centre.

The treatment information must not be unblinded except in medical emergencies when the appropriate management of the patient necessitates knowledge of the treatment randomization. If the treatment information is unblinded then the investigator(s) must document and report to ICON.

AZ retains the right to unblind the patient for SAEs that are unexpected and are suspected to be causally related to an investigational product and that potentially require expedited reporting to regulatory authorities. The data management committee (DMC) will keep treatment information strictly confidential and will not reveal any information to the study and project team.

5.4.3 Blinded treatment during the extension:

All patients will continue on the same blinded treatment (or open in cohort 2) as during the first 4 months of the study.

The sponsor and CRO personnel will have access the treatment codes after all patients in the 4-month study have been cleaned and database is locked (DBL) to allow for the planned analyses. However, the treatment codes will be strictly kept within the sponsor and CRO to safeguard the blinding of the monitors, investigators and patients and hence avoid possible bias in data handling. Thus, except for safety reasons, patients, investigators and study monitors in the field will have no access to the individual treatment codes until the study has been completed.

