5.7 Treatment compliance

The administration of all medication (including IP) should be recorded in the appropriate sections of the eCRF.

Treatment compliance, both regarding background metformin treatment and IP, will be assessed by tablet count. To be eligible for randomization, patients must have taken at least 75 % of their metformin tablets during the run-in period. In the statistical analysis, acceptable compliance is defined as having taken at least 75 % of the metformin doses and at least 75% of the IP doses during the randomized treatment period. Treatment compliance will be calculated as follows:

$$\text{Compliance} = \frac{\text{number of tablets dispensed} - \text{number of tablets returned}}{(\text{date of last dose} - \text{date of first dose} + 1) \times \text{number of tablets}}$$

The number of tablets in the calculation is the number of tablets that patients should have received each day, as per protocol.

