12.2.5 Compliance and Study Drug Exposure

The compliance of study drug will be completed for overall exposure per patient.

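### The per-protocol window and its compliance rule are not cut at month 4, so on a literal reading conduct in the extension can change who is in the supportive month-4 per-protocol analyses

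*Protocol*

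**What the plan says.** **Per-protocol set.** Section 12.1.1 builds it from full-analysis-set patients who "do not violate the protocol between randomization and study completion". Among the major deviations it lists "Patient is not compliant", with no period attached. The set is meant for the key efficacy variables. Section 12.2.6.1 uses it for the supportive observed-case analysis of the month-4 HbA1c change and, if the primary analyses are significant, for a centre/region-adjusted ANCOVA.

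**Compliance.** Section 5.7 requires at least 75% of metformin doses and "at least 75% of the IP doses during the randomized treatment period". The denominator of its formula counts days from first to last dose, and "The number of tablets in the calculation is the number of tablets that patients should have received each day, as per protocol". Section 12.2.5 adds: "The compliance of study drug will be completed for overall exposure per patient".

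**Is the extension randomized treatment?** The synopsis says that "those patients consenting also to the 2-month extension will receive randomized treatment for 6 months in total", and section 3.1.1 speaks of "up to 6 months randomized treatment". Section 5.5.2 also covers the extension in a paragraph headed as the randomized treatment period. Footnote o to Table 2 separates patients who complete the study at 4 months from those who consent to the extension, which implies that the latter complete later.

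**Unblinding.** Under section 5.4.3, sponsor and CRO personnel "will have access the treatment codes after all patients in the 4-month study have been cleaned and database is locked". Patients, investigators and monitors stay blinded until the study is complete.

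**The concern.** A per-protocol set for a month-4 endpoint should depend only on what happened up to month 4. A disallowed drug first taken in month 5, or tablets missed in month 6, cannot have affected an HbA1c already measured. If such events remove a patient, or if good compliance in the extension makes up for poor compliance before month 4, the set is selected on behaviour after the endpoint. That behaviour may differ by arm, and the per-protocol comparison can then be biased.

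There is also a timing problem. A patient still taking extension treatment at the 4-month lock has no date of last dose and has not completed the study, so the written rule cannot yet be evaluated for that patient. Under section 11.1 the CRO derives all data, and the CRO is unblinded at that point. The sponsor would have to settle membership with the codes known, or freeze the list at the lock and depart from the written definition. The protocol does not say which.

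**Working it through.** The protocol gives no figure on this point to reproduce. Its sample size is not in question: a standardised difference of 0.7/1.4 = 0.5 at 90% power and a two-sided 5% level needs 85.03 per group by the t-test, which rounds up to the stated 86.

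**Inputs**
- Visit 10 at day 120 and Visit 13 at day 180, each ±5 days (Table 2).
- Compliance threshold 75% (section 5.7).
- Assumption: the same number of tablets is due each day, so compliance is weighted by days, with 120 days to Visit 10 and 60 days in the extension.

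**Formula.** With compliance c1 to Visit 10 and c2 in the extension,

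overall = (120 × c1 + 60 × c2) / 180.

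**Non-compliant at month 4, compliant overall.** c1 = 70%, c2 = 90%: (84 + 54)/180 = 138/180 = 76.7%. The patient fails the threshold at the endpoint but is included.

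**Compliant at month 4, non-compliant overall.** c1 = 80%, c2 = 60%: (96 + 36)/180 = 132/180 = 73.3%. The patient passes at the endpoint but is excluded.

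**Break-even.** Setting the overall value to 75% gives c2 = (135 − 120 × c1)/60:

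| c1 to Visit 10 | c2 at which status switches |
|---|---|
| 65% | 95% |
| 70% | 85% |
| 80% | 65% |
| 90% | 45% |
| 100% | 25% |

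Taking the visit windows at their extremes (115 of 185 days, 125 of 175 days), the break-even is 83–88% for c1 = 70%, 63–67% for 80% and 38–50% for 90%.

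**Limit on rescue.** Without taking more tablets than prescribed (c2 at most 100%), overall compliance reaches 75% only if c1 is at least (135 − 60)/120 = 62.5%. A patient at 60% would need (135 − 72)/60 = 105%.

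**Other violations.** No arithmetic applies. Under the section 12.1.1 wording, one major deviation first occurring after Visit 10 but before the patient completes the study is enough to exclude.

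**The case against.** The strongest reply is that the protocol also supports a month-4 reading:
- Table 2 puts Visits 12 and 13 in a block apart from the randomized treatment period.
- Section 3.1.1 heads those visits separately, and section 5.5.2 has its own extension heading.
- Section 3.2 gives a total treatment period of 4 months, with the extension added for safety data.
- Section 12.2.10 contrasts extension data with the 4-month treatment period.
- The missing-data criterion in section 12.1.1 is tied to HbA1c at 4 months or the last visit.
- Sections 3.1.1 and 5.4.3 treat the 4-month study as a unit that is cleaned and locked before codes are released for the planned analyses.

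This stands as evidence of what was probably intended. A reader might infer that extension conduct necessarily decides membership, or that the set cannot be fixed before unblinding. The documents do not support either: a month-4 cut at the lock is compatible with much of the text. But Table 2 at most limits the term randomized treatment period. It leaves study completion and the date of last dose untouched, so the passages still conflict.

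It is also fair to say that section 12.2.5 describes a compliance summary and does not mention the per-protocol set, that a tablet count leaves little room for judgement influenced by the codes, and that early recruits may have finished the extension before the lock.

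Finally, detailed deviation windows are ordinary SAP content. Had the protocol been silent, there would be no finding. Here it states an end point, and that end point does not match the endpoint being analysed.

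**Conclusion.** The point holds as an inconsistent window, wrong for a month-4 analysis on its literal reading. Under that reading, 60 extension days can move a patient across the 75% threshold in either direction (70% to 76.7%, 80% to 73.3%), and a late violation can exclude a patient who had none at Visit 10. These figures rest on constant daily tablets and 120 and 180 days.

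The reach is limited. Only patients who enter the extension are affected, and the unblinding issue concerns only those still in it at the 4-month lock. The primary analysis, on the full analysis set with last observation carried forward, does not change. How many patients would be misclassified cannot be estimated, because the documents give no extension uptake, violation rate or compliance distribution. A reader might infer an imbalance between arms; that is possible, but nothing in the documents shows it. The change is worth making because it protects the per-protocol check on the primary result at no cost.

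**What to change.** 1. In section 12.1.1, end the violation window at Visit 10 or earlier discontinuation instead of study completion.
2. In section 5.7, compute the compliance used for the per-protocol set from first dose to Visit 10 or earlier discontinuation, for both IP and metformin, and summarise extension compliance separately. Align section 12.2.5 with this.
3. State, in section 12.1.1 or 5.4.3, that per-protocol membership is final before the 4-month codes are released to the sponsor and CRO.

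The cost is a few wording changes. No visit, procedure, treatment or sample size is affected.
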